physician once and then leave the system), we will include patients who have had 2 or more visits to a CSMG physician in the year prior to the study start date and at least 1 visit during the follow-up year. This will ensure that we have a relatively stable population, which will be critical in calculating the rates outlined in Aim 3 of the study. Prescribed opioid medications include: codeine, dihydrocodeine, tramadol, morphine, hydromorphone, oxymorphone, tapentadol, buprenorphine, methadone, oxycodone, fentanyl, and remifentanil.

Exclusion Criteria: We will exclude individuals less than 18 years of age because the communication comparators include Choosing Wisely and CDC guidelines that do not address the use of opioids in minors. Exclusion criteria also include individuals with treatment for chronic pain during (1) active cancer treatment, (2) palliative care, or (3) end-of-life care. Patients who do not see their primary care provider during the study period will be excluded retroactively from the study.

D3. Study Population. We will conduct this study in the Cedars-Sinai Medical Network, a large, urban, integrated delivery system serving a diverse population. The Cedars-Sinai Medical Network services a large cohort reflective of the national population with regards to insurance coverage as well as chronic pain prevalence and opioid use.⁸⁵ A quality improvement claims-based analysis of patients served by the network found that 30% of individuals at Cedars-Sinai have a chronic pain condition, approximately 22,800 patients in total, consistent with national chronic pain prevalence estimates.⁸¹ Using national chronic pain prevalence data, we estimate that the population for this study is distributed by race and ethnicity as described in Table 1: (RQ3, RQ4)

Table 1. Estimated Race-Ethnicity Distribution of the Study Population for Proposed Study		
	National Chronic Pain Prevalence Data ⁸¹	Estimated Study Population Race-Ethnicity Distribution
Non-Hispanic White	81%	18468
Non-Hispanic Black	8%	1824
Hispanic	5%	1140
Asian	1%	228
Mixed Race	3%	684
Other	3%	684

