- (1) *Discussion of Risks and Benefits of Opioid Analgesics as Long-Term Therapy for Patients with Chronic Pain and Establishment of a Treatment Goal.* This alert is triggered whenever a refill for a long-acting or extended-release opioid is entered or when any new opioid prescription is ordered.
- (2) *Evaluation of Risk Factors for Opioid-Related Harms.* This alert is triggered whenever there is an existing diagnosis of prior substance abuse disorder, history of overdose, history of sleep apnea, renal or hepatic insufficiency, age over 65 years, or a diagnosis of depression, anxiety disorder, or Post-Traumatic Stress Disorder in the setting of opioid use.
- (3) *High-Risk Opioid Co-Prescribing: Co-Prescribing of Benzodiazepines and Opioids.* This alert is triggered whenever an order for a benzodiazepine is entered in the setting of a preexisting opioid prescription, or vice versa.

Figure 2 presents a schematic demonstrating the process flow for a CDS alert, using the example of the co-prescribing alert. The process begins when a provider places the medication order in the EHR. The Choosing Wisely algorithm, powered by Stanson Health, a CDS developer used by Cedars-Sinai to power its EHR alerts (www.StansonHealth.com), then evaluates over 30 patient-level data elements to determine whether an alert should be triggered. If there is evidence of potentially inappropriate co-prescription, then the EHR displays a “pop-up” reminder with language supported by Choosing Wisely guidelines. The provider may override the alert by selecting one of several pre-populated reasons (e.g. “end-of-life care”) and the system records the rationale. The system also allows the provider to offer open-ended comments explaining the reason for override. Conversely, the provider may choose to cancel the order and back out from initiating a prescription. Through an analytics dashboard supported by Stanson Health and already used by our health system to monitor system performance with Choosing Wisely alerts, we will track: (1) which provider activated the alert, (2) whether the provider overrode the alert or canceled the order, and (3) for which patient

the alerts were triggered. In this manner, the system offers hard metrics that are already embedded and operating within our EHR data analytics system, offering real-time process measures for the CDS arm.

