5. *Comparison intervention practitioner expertise.* Pragmatic trials do not standardize which and how practitioners implement the intervention. In this case, we will cluster-randomize all of the PCPs in our practice to the intervention and will not standardize who or how they will implement the communication strategies. Score = 5.
6. *Follow-up intensity.* Purely pragmatic trials do not have any formal follow-up visits of the individuals and use passive administrative databases to detect outcomes. Given the importance of patient-reported outcomes in this study, we will use a combination of passive and active follow-up methods to ascertain outcomes; these have low respondent burden and only require the completion of short questionnaires. Score = 4.
7. *Primary trial outcome.* Pragmatic trials select outcomes that are meaningful to study participants. Our main outcome will be pain interference, or how pain interferes with a patient's daily life, an outcome identified as meaningful by our patient partners. This outcome is important because while we seek to prevent inappropriate overuse of opioids, the flip side – discontinuing appropriate use of opioids – should also be prevented. The net outcome – pain interference – reflects a balance between inappropriate overuse and underuse of effective pain treatments. Score = 5.
8. *Participant compliance with "prescribed" intervention.* Pragmatic trials measure little or no patient "compliance" with the intervention. When we administer the questionnaires, we will ask whether individuals have received and read the PEAT materials via REDCap but we will not measure adherence to or use of PEATs. Score = 4.
9. *Practitioner adherence to study protocol.* Trials with pragmatic designs use unobtrusive or no methods to measure practitioner adherence to the study protocol. We will measure when and for whom the CDS alerts are activated, but will not report feedback to providers. Score = 4.
10. *Analysis of primary outcome.* PRECIS notes that pragmatic trials include all enrolled patients in the final analysis and there is no separation of the intention-to-treat (ITT) vs. per protocol (PP) patients. We will conduct both ITT and PP analyses for sensitivity analysis purposes. We will ask patients whether they received and read the PEAT materials and will examine when the CDS alerts were fired and for which patients to conduct a PP analysis. Score = 3.

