E4.b. Unit of Randomization. We will randomize the study on the provider level. We will use a random number generator to assign offices to study arms, and will employ multi-level hierarchical models to adjust for clustering within the physician level, described in more detail below.

E4.c. Study Design Overview.

We will auto-enroll all eligible patients to participate in the pragmatic trial and will administer baseline questionnaires as further detailed in the Recruitment Procedures and Outcome Measurement sections below. Patients within the physicians randomized to the CDS arm will not receive the PEAT materials; their physicians will receive the Choosing Wisely alerts via the EHR (Epic Systems, Verona, Wisc.) when appropriate. Patients within the physicians randomized to PEAT will receive the engagement materials via REDCap two days prior to their PCP office visit, supplemented by duplicate paper copies sent via express delivery. For both study arms, patients will receive Clinician and Group Consumer Assessment of Healthcare Providers and Systems (CG-CAHPS) one day after their office visit. They will receive the PROMIS questionnaires every month throughout the study period. We will track follow-up visits through the EHR reports. In all instances, patients may refuse to participate by either not using the PEATs sent via REDCap, or not completing outcome questionnaires.

3. Analysis, Dissemination, and Implementation. In Year 3, we will conduct the statistical analyses and will collaborate with our patient partners to determine the implications of the study results. We present our Dissemination and Implementation plan in full detail below.

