E4.e. Data Collection (RQ-2). Upon auto-enrollment, we will extract the following variables from the electronic health record: chronic pain condition, length of time with chronic pain diagnosis, race and ethnicity, language, marital status, history of pharmacologic treatment, surgical history related to chronic pain condition, past injuries related to chronic pain condition, and length of time with current primary care provider¹³⁷. When the intervention period is initiated, all eligible patients who have any follow-up visits during this 12-month period in both study arms will be sent the questionnaires. We will also capture depression scores via the Patient Health Questionnaires -PHQ-2 and/or PHQ-9 in the EHR. Furthermore, to determine if conversations about opioid medications took place during the visit that was

informed by either the CDS or the PEATS, we will conduct a structured review of a random sample of charts from both study arms.

E5. Statistical Analysis

E5.a. Descriptive and Exploratory Analyses. We will use frequencies and means for univariate descriptive analyses. We will use chi-square tests and paired t-tests to determine whether there are differences between the two study arms; using these bivariate analyses, we will identify covariates and patient- and physician-level moderators to use in the regression models. We will also consult with our Patient Partner to ensure that all appropriate patient-level covariates are included in the final models.

E5.b. Multi-Variate Regression Models. To evaluate the effectiveness of the comparators on the selected outcomes, we will use hierarchical linear regression models to measure changes in the outcomes over time using growth modeling statistical techniques¹³⁸ and will adjust for clustering at the patient, provider, and provider office level. Growth modeling allows the testing of individual differences in outcomes over time. In this study, we will examine HRQOL and communication scores over 12 months for the two study arms. We will adjust for patient- and provider-level covariates to account for potential confounders and also to identify whether there is heterogeneity of the treatment effect (see below). The proposed models are outlined here. We will test both fixed effects and random effects.¹³⁹ (IR-3):

Primary Outcome: Model 1: Hierarchical Linear Model (Longitudinal Analysis)

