b. Statistical Methods to Handle Missing Data and Sensitivity Analyses. If the data is not missing at random, we will use multiple imputation techniques to impute missing data for respondents (MD-2). We plan on using the *mi impute mvn* command in Stata and will generate 20 datasets compatible with the regressions planned for the final analyses. To insure that the imputation has proceeded as expected, we will visually inspect parameters from successive iterations of the model to determine if they have reached a stationary distribution. We will conduct sensitivity analyses with the dataset that includes imputed data as well as with a dataset that does not include imputed data to determine the effect of the multiple imputation and plan on reporting both results. These precautions will serve to identify autocorrelation in the imputed data and allow for proper maintenance of uncertainty in imputed values (MD-3).

c. Reporting Reasons for Dropout and Missing Data. We will drop data from patients who do not have any visits with their PCP during the intervention period or are lost to follow-up, but will compare descriptive statistics for these patients to patients with at least one visit to their PCP for sensitivity analysis (MD-4, MD-5).

E9. Project Milestones and Timeline.

During the first 3-6 months of the study project, we will train the project staff, refine the study protocol, develop the data dictionaries, and obtain IRB approval. We will hold monthly meetings with our patient partners to finalize the study design and discuss issues related to IRB approval. In Year 1, Q4, we will passively enroll eligible patients in the two study arms. In the 4 weeks before the intervention period, we will send baseline questionnaires via REDCap. In Year 2, we will begin the intervention. We will conduct weekly reports from our EHR data warehouse to determine enrolled patient visits. Enrolled patients will be sent CG-CAHPS survey one day after each primary care visit. Enrolled patients will also receive the PROMIS questionnaires once a month. We will perform monthly checks to assess the completeness of data to minimize missing data and will complete one set of interim data analyses in Year 2 to assess whether there are any issues with missing data. Full data analysis will

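### Patients with no follow-up visit are dropped after randomisation, which conflicts with the promised ITT analysis and creates a selection-bias risk of unknown size

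*Combined protocol and SAP*

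**What the plan says.** D2 makes eligibility depend partly on the future. Besides two or more visits in the year before the study, a patient needs "at least 1 visit during the follow-up year". The reason given is a stable population for the Aim 3 rates. The exclusion criteria then add: "Patients who do not see their primary care provider during the study period will be excluded retroactively from the study."

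The Missing Data section (E7, part c) carries this into the analysis and widens it: "We will drop data from patients who do not have any visits with their PCP during the intervention period or are lost to follow-up". The safeguard is in the same sentence: the plan "will compare descriptive statistics for these patients to patients with at least one visit to their PCP for sensitivity analysis".

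The visit is worded in three ways: a CSMG physician in the follow-up year and the PCP in the study period (both D2), and the PCP in the intervention period (E7, part c).

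On the analysis set, item 10 of the PRECIS list says: "We will conduct both ITT and PP analyses for sensitivity analysis purposes." The same item cites inclusion of every enrolled patient as the pragmatic norm. The plan defines no ITT set and does not name the main analysis set.

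On who is surveyed, E4.e says that "all eligible patients who have any follow-up visits during this 12-month period in both study arms will be sent the questionnaires". E4.c and E9 describe monthly PROMIS questionnaires with no visit condition.

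**The concern.** Randomisation protects a comparison when membership of the analysed groups cannot depend on the assigned arm. Here membership depends on something that happens during follow-up, and the plan itself gives reasons why arm could affect it:

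- PEAT patients "will receive the engagement materials via REDCap two days prior to their PCP office visit", so a patient can read the materials and then cancel.
- CDS acts at order entry, not only at a visit: "This alert is triggered whenever a refill for a long-acting or extended-release opioid is entered".
- The rationale for Aim 1 links patient activation to use of care, and PEAT is the activation arm.

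The executive summary asks whether a strategy might cut opioid prescribing yet leave patients with poorer quality of life. Patients who disengage from care altogether after contact with either tool bear directly on that question, and the rule removes them. At stake are pain interference (Model 1), the other PROMIS outcomes (Model 3) and the prescribing outcomes (Models 4 and 5).

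**Working it through.** **1. Time order.** Attachment C-R finalises the eligible list on 5/30/2017, completes randomisation on 7/30/2017 and starts the intervention on 1/1/2018. Under E4.c all eligible patients are auto-enrolled. A visit in the follow-up year can be known only after all of these steps, so both D2 conditions and the E7 rule select after randomisation.

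**2. Conflict with ITT.** If D2 and E7 part c are applied, every analysis set contains only patients with at least one visit who were not lost. The ITT analysis in PRECIS item 10 then has no all-enrolled population to work on. Dropping losses also sits badly with E7 part a, which relies on maximum likelihood under missing at random. That method can use the partial data of patients who are lost; the rule discards them.

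**3. Data available without a visit.** Pharmacy data are pulled for passively enrolled patients (Attachment C-R). PROMIS would be available under E4.c and E9 but not under E4.e. CG-CAHPS is sent one day after a visit, so it does not exist for non-visitors.

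**4. Size of the possible bias.** The point rests on no figure in the plan. Let q be the share removed in an arm, and d the removed-minus-retained difference in mean outcome, in SD.

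Full-arm mean = (1 − q) × retained + q × removed = retained + q·d, so the retained mean is off by q·d. If the arms as randomised are comparable and neither tool changes the outcome, then

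bias in the arm difference = q·d in one arm − q·d in the other, in absolute size.

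With the same d in both arms this is (difference in q) × d. The documents give neither q nor d, so the values below are assumed. The standard error implied by the E5.c design (0.3 SD, 90% power, 5% level taken as two-sided) is 0.3 / (1.960 + 1.282) = 0.0925 SD.

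| Difference in q (assumed) | d (assumed) | Shift, SD | Share of 0.3 SD | Nominal 5% error becomes |
|---|---|---|---|---|
| 0 | any | 0 | 0% | 5% |
| 5 points | 0.5 | 0.025 | 8% | 5.8% |
| 10 points | 0.5 | 0.05 | 17% | 8.4% |
| 10 points | 1.0 | 0.10 | 33% | 19.1% |

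Equal shares alone do not protect. If 10% are removed in each arm, 0.5 SD worse in one and no different in the other, the shift is 0.10 × 0.5 − 0.10 × 0 = 0.05 SD.

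**5. Cost of keeping everyone.** If a share v of patients never visits and gets no effect, 0.30 SD becomes 0.30 × (1 − v), and the 320 per arm stated in E5.c becomes 320 / (1 − v)².

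- v = 10%: 0.27 SD, 396 per arm.
- v = 20%: 0.24 SD, 500 per arm.
- The target of 960 (480 per arm) keeps 90% power up to v = 1 − √(320/480) = 18%, but only if none of the 50% inflation is needed for loss to follow-up.

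The 320 is taken as stated. It cannot be reproduced, because no cluster size is given: 234 per arm before clustering, with ICC 0.02, gives 267 at 8 patients per PCP (640/80) and 320 at about 19.5.

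**The case against.** The strongest defence is that the rule is identical in both arms, that much of each intervention is delivered around a visit, and that non-visitors mostly add noise. Removal also needs no visit at all in the period, among patients who had at least two the year before, so the share may be small. E7 part c does at least compare dropped with kept patients. All of this stands as a limit on size. It does not restore the randomised groups: a common rule can select differently in each arm, and a descriptive comparison not stated by arm would not show it.

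Several stronger readings are tempting but not supported:

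- *The ITT analysis is impossible.* This is true only while the drop rule stands. Once it goes, an all-enrolled analysis is possible for prescribing, and for PROMIS if E4.e is reconciled.
- *Any patient refused a refill who does worse is deleted.* One visit in the period is enough to be kept. The read-and-cancel and refill-without-visit routes are possible, but the documents give no frequency for either.
- *The enrolment letter in E4.d lets patients act on their arm.* That opt-out concerns receiving materials, not attending, and does not show that patients know their arm. The time order is argument enough.
- *One arm is being flattered by a known amount.* Only the between-arm difference in q·d matters, and its direction and size are unknown.
- *Removing the rule repairs every outcome.* It cannot do so for CG-CAHPS. For PROMIS, E4.d expects only about 30% of 4,000 eligible patients to complete all questionnaires, so selection by response remains.

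**Conclusion.** The concern holds as a conflict within the plan and a risk of bias, not a demonstrated bias. Selection on a post-randomisation visit, and on not being lost, is written into both eligibility and analysis and leaves no all-enrolled comparison for the promised ITT analysis. The possible shift runs from zero, if removal is the same in both arms in share and kind of patient, through 0.025 SD to 0.10 SD under the assumed inputs, with no upper limit set by the documents. It should be settled before follow-up, because PROMIS scores never requested from non-visitors cannot be recovered later. The stated reason does not require the rule, since the prior-year visit criterion already addresses stability using pre-randomisation data.

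**What to change.** 1. In D2, delete the follow-up-visit condition and the retroactive exclusion. In E7 part c, delete the drop rule for non-visitors and for patients lost to follow-up.
2. Define the ITT set as all patients eligible on pre-randomisation data, including two or more visits in the prior year, analysed by the assigned arm of their baseline PCP. State the date of the list, since Attachment C-R finalises it on 5/30/2017 but counts enrolment to 12/31/2018.
3. Use this set for pain interference, the other PROMIS outcomes and the Aim 3 prescribing outcomes. Keep the available data of patients lost to follow-up under the planned likelihood model.
4. Reconcile E4.e with E4.c and E9 so that PROMIS goes to every enrolled patient regardless of visits.
5. Report the set with at least one visit as a sensitivity analysis, using one definition of the visit, and give visit rates by arm.
6. State that the CG-CAHPS comparison is conditional on attendance, and that PROMIS non-response is a separate issue.

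The cost is protocol and SAP wording, more questionnaires to send, and some dilution from unexposed patients. The sensitivity analysis in step 5 helps to gauge that dilution, though it remains open to the selection described above.

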E4.d. Recruitment Procedures (PC-2). Patients meeting inclusion criteria who are managed by one of the 80 participating PCPs at the Cedars-Sinai Medical Network will be auto-enrolled in the study. Patients will receive a written notification via mail of their inclusion in the study and at that time they will be told about the study details, including research procedures and requirements for follow-up, as well as the risks and benefits of study participation. At this time, patients will have the opportunity to actively opt out of receiving the education materials (if they are randomized to PEAT arm). Patients who do not opt out will receive education materials and their care will proceed as usual. Patients who are passively enrolled will receive the study questionnaires via REDCap. We estimate that out of the 4,000 patients eligible for the study (calculated from a quality improvement project based on claims data), approximately 30% will complete all of the questionnaires, which is in line with our sample size calculations. Once the patients complete monthly questionnaires, we will provide a \$5 gift card for filling out the enrollment survey. We have budgeted \$25 per patient as

a financial incentive for completing the questionnaires (Appendix I, **Table 1 for Recruitment Plan** and **Table 2 for Passive Enrollment Estimates**).

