Attachment C-R: Milestone Schedule

	Milestone Name	Description	Projected Completion Date
A	Project Start Date	-	3/13/2017
B1	Stakeholder engagement meeting	Stakeholder engagement kick-off meeting	3/30/2017
B2	Patient eligibility data pulls	EIS Data Analyst to create a list of eligible patient population	4/30/2017
B3	Study protocol completed	Final trial protocol completed - submit a copy to PCORI	5/30/2017
B4	Patient eligibility data pulls	EIS Data Analyst to finalize list of eligible patient population and other data pulls	5/30/2017
B5	IRB Approval Obtained	Obtain IRB approval for study and submit approval letters to PCORI	7/30/2017
B6	DSMB Meeting 1	Set safety protocols and standards for data safety monitoring	7/30/2017
B7	Integration of questionnaires into patient portal	EIS Data Analyst to integrate questionnaires into MyCSLink	7/30/2017
B8	Select and register project at appropriate site for the study design (Clinicaltrials.gov, RoPR, or other as approved by PCORI before study start date)	Study Identification Number and the Primary Research Completion Date must be sent to PCORI.	7/30/2017
B9	Randomization of clinic sites	Randomization of Cedars-Sinai network offices completed; 50% to CDS arm and 50% to PEAT arm of trial	7/30/2017
B10	Passive patient recruitment begins	Passive data enrollment begins for study participants (N=960) / Study begins	8/1/2017
B11	Pharmacy data collection begins	EIS Data Analyst to begin pull data for passively enrolled patients on pharmacy data for data monitoring purposes	8/1/2017
B12	Patient baseline questionnaires	Enrolled patients begin filling out PROMIS patient reported outcome questionnaires	8/1/2017
B13	Stakeholder engagement meeting	Stakeholder engagement meeting to update on IRB submission and patient eligibility protocols and baseline data collection	8/31/2017
B14	Engagement Update	For the 6-month time intervals (i.e., 6 months, 18 months, 30 months, etc. but not at 12 months or 24 months), provide specific examples of the impact of engagement on project activities during the reporting period. Report this in the Engagement Report section of the PCORI interim progress report.	9/13/2017
B	Report Submission	Submit 6-month Interim Progress Report, Using PCORI Interim Progress Report Template	9/13/2017
C1	Study intervention begins	Study intervention begins	1/1/2018
C2	Stakeholder engagement meeting	Updates on study implementation	2/28/2018

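### Units are split 50:50 by random number generator with no stratified or covariate-constrained allocation described: modest avoidable imprecision with 80 PCPs, material if the unit is a small number of offices

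*Combined protocol and SAP*

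**What the plan says.** On method, E4.b says "We will use a random number generator to assign offices to study arms". Milestone B9 in Attachment C-R, dated 7/30/2017, adds "Randomization of Cedars-Sinai network offices completed; 50% to CDS arm and 50% to PEAT arm of trial". Nothing in the available text stratifies, matches, minimises or constrains the allocation on any characteristic of the PCP or office.

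On the unit, the same E4.b paragraph opens with "We will randomize the study on the provider level". Item 5 of the PRECIS list in section E4 says "we will cluster-randomize all of the PCPs in our practice to the intervention". B9 speaks of offices. E4.d gives the number of physicians: patients "managed by one of the 80 participating PCPs at the Cedars-Sinai Medical Network will be auto-enrolled in the study". No number of offices is given.

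On timing, milestone B4, dated 5/30/2017, reads "EIS Data Analyst to finalize list of eligible patient population and other data pulls". Under D2, eligibility is itself defined by opioid prescriptions and by two visits in the prior year. Milestone B11 starts the study's pharmacy pulls on 8/1/2017, two days after randomisation.

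On analysis, E5.b adjusts for patient and provider covariates. The lists for Models 1 and 2 include physician gender, physician years of practice, benzodiazepine use and baseline HRQOL, and Models 3 to 5 take over the Model 2 list. Baseline opioid dose, baseline high-dose status and a PCP's prior prescribing rate are on none of the lists. Models 4 and 5 add a differences-in-differences analysis under other analyses.

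**The concern.** A cluster trial with few units cannot rely on simple chance to balance them, and here the data needed for balancing are scheduled to exist, or can be obtained, before the draw. An uneven spread of panel sizes costs some precision. An uneven spread of prescribing style, physician gender or experience widens the uncertainty of the comparison and makes the result harder to defend.

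The exposure is greatest in Aim 3. Its outcomes are prescriptions above 90 MME and opioid-benzodiazepine co-prescription, and a PCP's habits before the trial are likely to predict both. If the arms start apart on high-dose prescribing, no listed covariate in Model 4 deals with it directly. The covariate lists are also only potential ones: E5.a selects from them by bivariate comparison of the arms, which is weaker than balance fixed in advance.

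**Working it through.** **Inputs from the plan.** 80 PCPs and 4,000 eligible patients (E4.d), so 4,000/80 = 50 per PCP; a 50:50 split (B9, stated for offices); ICC 0.02 and a target difference of 0.3 SD (E5.c).

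**Assumed, because the plan does not give them.** A 40/40 split if PCPs are the unit; a panel-size CV of 0.4 to 1.0; 10, 20 or 40 units if offices are randomised. The plan states no expected imbalance, so there is no figure of its own to reproduce.

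**1. Share of eligible patients in one arm.** With k units split equally, the SD of an arm's share is about CV/(2√k). For k = 80:
- CV 0.65: 1.96 × 0.65/(2√80) = 0.071, so 43-57%
- CV 0.4: 1.96 × 0.4/(2√80) = 0.044, so 46-54%
- CV 1.0: 1.96 × 1.0/(2√80) = 0.110, so 39-61%

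Simulation gives the same ranges.

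**2. What that costs in precision.** Take a 43:57 split of 4,000 patients over 40 PCPs per arm: 1,720 and 2,280 patients, with mean panels of 43 and 57. The design effects 1 + (m − 1) × 0.02 are 1.84 and 2.12. The variance of the arm difference is proportional to 1.84/1,720 + 2.12/2,280 = 0.00200, against 2 × 1.98/2,000 = 0.00198 when balanced. The increase is 1.0%. The same sum for 960 patients gives 1.6%. Either is under 1% in the standard error.

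**3. Difference in a unit-level trait.** In between-unit SDs, the 95% limit is 1.96 × 2/√k: 0.44 for k = 80, 0.62 for 40, 0.88 for 20 and 1.24 for 10. Simulation, which standardises by the realised SD, gives 0.44, 0.62, 0.89 and 1.26.

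**4. What constraint would achieve.** In simulation with panel-size CV 0.6, 2,000 equal-split allocations were scored on patient share and one unit-level trait, and the best 10% were kept. The limits and shares are 95th percentiles.

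| Units | P(trait gap > 0.25 SD), 50:50 only | P(gap > 0.5 SD), 50:50 only | Trait limit, 50:50 only | Trait limit, constrained | Larger arm's share, 50:50 only | Larger arm's share, constrained |
|---|---|---|---|---|---|---|
| 80 | 26% | 2.5% | 0.44 SD | 0.09 SD | 56.4% | 51.4% |
| 40 | 43% | 11% | 0.62 SD | 0.13 SD | 58.8% | 51.9% |
| 20 | 58% | 26% | 0.89 SD | 0.20 SD | 62.0% | 52.7% |
| 10 | 69% | 43% | 1.26 SD | 0.30 SD | 65.4% | 54.1% |

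**5. Scale for pain interference.** The 95% chance range of the arm difference from cluster effects alone is ±1.96 × √0.02 × 2/√k. This is ±0.06 SD with 80 units (21% of the 0.3 SD target), ±0.12 SD with 20 (41%) and ±0.18 SD with 10 (58%).

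**6. Size of the allocation space.** Ten offices allow 10!/(5!5!) = 252 equal splits, so keeping the best 10% leaves about 25. Twenty offices allow 184,756.

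**The case against.** The strongest reply is that a 50:50 random allocation of 80 PCPs is valid as it stands. Chance imbalance is not bias, and a correct cluster-level standard error already covers it. Steps 2 and 5 show that for panel size and for pain interference the loss with 80 PCPs is small. Physician gender, years of practice and benzodiazepine use are already candidate covariates, and the differences-in-differences analysis removes stable baseline differences in prescribing. All of this stands, and it limits the size of the point. It does not close it. The differences-in-differences analysis is a supplement to Models 4 and 5, baseline high-dose status is not a listed covariate, and none of this helps much if the unit turns out to be a few offices.

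Four stronger readings are tempting, and the documents do not support them.
- A reader might infer that allocation is wholly unrestricted. B9 sets an even split, which removes the risk of unequal unit numbers.
- A reader might infer that each PCP's prescribing is known before the draw. Eligibility does use opioid prescriptions, but the study's pharmacy pulls start after randomisation and no per-PCP summary is mentioned. The most that can be said is that it could be pulled in time. The analysed patients also depend on a follow-up-year visit and on questionnaire response, which no baseline list can balance.
- A reader might set a chance baseline difference in high-dose rates against the detectable difference for Aim 3, as a further threat. A detectable difference computed with the ICC already contains that between-PCP variation, so the comparison counts it twice.
- A reader might conclude that no balancing exists anywhere. Appendix I and parts of section E4 are not in the available text, so the claim is limited to what that text describes.

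**Conclusion.** The point holds as a cheap improvement to the design, not as a flaw that invalidates the trial. The stated method leaves chance imbalance that could be largely removed before randomisation. With 80 PCPs split 40/40 it is modest: about 43-57% of patients in one arm at an assumed CV of 0.65, and a 95% limit of 0.44 between-PCP SD on a trait, which constraint would cut to about 0.09. With an assumed 20 or 10 offices the trait limit is about 0.9 or 1.3 SD, which is material.

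Which case applies cannot be settled from the documents, because E4.b, the PRECIS list and B9 disagree on the unit and no office count is given. The panel-size CVs and office numbers are assumptions. The 80 PCPs, the 4,000 patients, the ICC and the dates are the plan's own. The consequence is lost precision and credibility, mainly for Aim 3.

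**What to change.** 1. State one unit of randomisation and the number of units, and bring E4.b, PRECIS item 5 and milestone B9 into agreement.
2. Replace the random-number sentence with 50:50 covariate-constrained randomisation. From the B4 pull, compute for each unit the number of eligible patients, the percentage with prescriptions over 90 MME and the percentage co-prescribed a benzodiazepine. Physician gender and years of practice may be added. Set balance limits in advance and draw one allocation at random from those that meet them.
3. Prespecify the balancing factors as covariates instead of leaving them to bivariate selection, and add each patient's baseline high-dose and co-prescription status to Models 4 and 5.

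The cost is a few hours of programming, a baseline medication pull moved ahead of the draw, and a few more model terms; no extra patients are needed. The number of acceptable allocations must be checked. That is trivial with 80 PCPs, but with about 10 offices the limits have to be loose and only a few unit-level terms can be supported. Items 1 and 2 have to be settled before the allocation is drawn. If it already has been, item 3 is the part that can still be adopted, before outcome data are examined.
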